To better understand the effects of renin-angiotensin aldosterone system (RAAS) on renal function in human heart failure, we defined the renal hemodynamic and humoral actions acute AT1 blockade (Losartan, 50 mg orally) vs placebo in combination with Furosemide in 10 NYHA II-III CHF patients in a double-blind placebo controlled cross-over study. Furosemide with placebo resulted in increased sodium excretion (212±66 to 425±82 µEq/min, p<0.05) associated with reductions in both renal blood flow (307±30 to 246±23 ml/min, p<0.05) and glomerular filtration rate (76±8 to 63±6 ml/min, P<0.05). (Figure 3) However, after 4 hrs, there was a significant reduction in sodium excretion as compared to baseline (212±66 to 104±21 µEq/min, p<0.05). In contrast, Lasix with Losartan resulted in a similar increase in sodium excretion without reductions in renal blood flow and glomerular filtration rate. Furthermore, after 4 hrs, sodium excretion was greater as compared to the placebo group. Plasma aldosterone decreased only in the losartan group. This study suggests that the RAAS via AT1 receptors may be involved in the detrimental renal effects of diuretics in CHF. Therefore, antagonizing the RAAS in CHF patients on diuretics may improve renal function, which is an important predictor of survival in human CHF.

RESEARCH DESIGN AND METHODS

Objectives

The main objective of this study is to translate the findings of the applicant's study in experimental CHF to human CHF and determine the modulating actions of chronic AT1 receptor blockade in addition to ACE inhibitor, beta-blocker and furosemide on cardiorenal and humoral function in humans with compensated CHF and renal dysfunction. Preliminary studies completed by the applicant in experimental CHF have shown improvement in left ventricular function and enhanced renal function with AT1 receptor blockade. (see Preliminary studies) Furthermore, the applicant also completed a study in human compensated CHF demonstrating that acute AT1 blockade prevented the detrimental renal effects of furosemide therapy. (see Preliminary studies)

Hypotheses

1. Chronic AT1 receptor blockade in subjects with compensated CHF and renal dysfunction will improve renal function with increased sodium excretion, glomerular filtration rate and effective renal plasma flow as compared to the response of placebo-treated subjects.

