After an equilibration period of 45 minutes, urine and blood samples are collected at 30-minute intervals for 3 periods to determine the baseline GFR and urinary sodium excretion (UNaV). Blood pressure will be measured at 20-minute intervals by using automatic blood pressure cuff, and heart rate will be continuously monitored. Urinary samples for determination of volume, sodium, potassium, lothalamate, and PAH, will be obtained at the end of each clearance period. Venous blood samples for lothalamate, PAH and sodium will be obtained at the middle of each clearance period. During the first clearance, venous blood samples for renin, aldosterone, angiotensin II, ACE, ACE 2, angiotensin 1-7, ANP, BNP, Bradykinin, NO, DNA, protein and cGMP will be obtained and urine samples for cGMP will also be obtained. BUN will also be run. Echocardiography will be performed after these baseline clearances as described.

At the completion of the baseline assessments, subjects will be randomized to Candesartan or placebo group. The randomization schedule will be provided by the Division of Biostatistics, implemented by the Mayo Pharmacy and administered by the CRU staff. The investigators and the CRU staff will not be aware of the randomization arm the subject is assigned to.

Subjects will receive the first dose of study drug in the CRU. Subjects will be started at 4 mg once a day. Thereafter, both blood pressure and heart rate (by electrocardiography) will continue to be monitored for the next 4 hours. If the patients develop symptomatic hypotension as defined by systolic blood pressure of ≤ 85 mmHg, with lightheadedness, dizziness or visual symptoms after the first dose of the medication in the CRU, the patient will be excluded from the rest of the study. The dose will be doubled every 14-18 days as tolerated to a goal of 16 mg a day or highest dose tolerated. Patients will get blood draw 7-10 days after each dose increase to measure plasma creatinine and potassium until target dose is achieved. *If there should be a potassium result <3.5 or >6.0 , subjects will need to have labs redrawn the same day.* Thereafter, subjects will get blood draws every 4 weeks (± 3 days). If distance indicates, blood draws will be arranged at the participants local clinic. Subjects will also have access to a 24-hour phone number should they have any questions or develop any side effects. They will be instructed to measure their blood pressure weekly and

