record it, along with heart rate and weight. They will also receive a weekly phone call to review status. During the study, if patient develops symptomatic hypotension as defined above or an increase of plasma creatinine of > 0.3 mg/dL or hyperkalemia > 5.7 meq/ml, the dose will be reduced by 50%. If those parameters persist, the dose will be decreased further by 50%. At the discretion of the investigator, the medication can be discontinued.

At the end of the twelve-week study period (± 7 days), subjects will be admitted to the CRU again. A 6-min walk, MLHFQ, echocardiography, renal clearance, humoral determination and renal functional reserve will be performed in the same manner as the baseline study. Subjects will also perform a 24-hour urine collection the day prior to their return visit for determination of sodium excretion, creatinine clearance and microalbuminuria. Subjects will be dismissed after the renal clearance study.

iii) Sample size and statistical analysis

The sample size calculation and statistical analysis have been designed in collaboration with the Division of Biostatistics, ([name] and [name]).

The **primary analysis** for this study will be a comparison of the parameters of interest between the AT1 receptor blockade group and placebo. This analysis will be completed using a two-sample t-test comparing the change from baseline to the latest time point available. In addition to this primary analysis, if complete or near complete data is available, a secondary analysis will be completed using all data from baseline to the latest available time point. The groups will be compared in this analysis using a 2 factor repeated measures analysis of variance. Values will be expressed as the mean \pm SE. A statistically significant difference will be considered to be present when $p<0.05$.

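### The primary t-test on change is valid, but adjusting for the pre-randomization baseline would give a small, conditional gain in precision at almost no cost

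*Combined protocol and SAP*

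**What the plan says.** Section iii (Sample size and statistical analysis) defines the primary analysis in one sentence: "This analysis will be completed using a two-sample t-test comparing the change from baseline to the latest time point available". No covariate is named there or elsewhere, and no correlation between baseline and week 12 is given. If data are complete or nearly so, a secondary analysis follows: "The groups will be compared in this analysis using a 2 factor repeated measures analysis of variance". The tested term (group, time or their interaction) is not named.

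Section ii (Study protocol) fixes the timing: "At the completion of the baseline assessments, subjects will be randomized to Candesartan or placebo group". Hormones are sampled once per visit: "During the first clearance, venous blood samples for renin, aldosterone, angiotensin II" and the other humoral markers. GFR and sodium excretion come from three 30-minute clearance periods. Week 12 repeats the baseline set: "A 6-min walk, MLHFQ, echocardiography, renal clearance, humoral determination and renal functional reserve will be performed in the same manner as the baseline study". Creatinine and potassium are also drawn between these visits: "Patients will get blood draw 7-10 days after each dose increase to measure plasma creatinine and potassium until target dose is achieved".

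The sample size paragraph assumes a placebo SD of change half the treated SD, on the argument that treated patients are a mix of those who respond and those who do not. It states both a 2:1 allocation and 38 patients per group.

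**The concern.** A change score subtracts the whole baseline value, which sets its slope at 1. If follow-up values regress toward the mean, the true slope is below 1, and a model that estimates it gives a narrower interval for the same treatment difference. Because baseline is measured before randomization, adjusting for it is legitimate and needs no new data. At stake are interval width and power for effects smaller than those the plan sized for.

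A smaller matter concerns the secondary ANOVA. For an outcome with one value at each of two visits, it may return the primary result under another name, and a reader could count one test as two agreeing analyses.

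**Working it through.** **1. The plan's own figure.** Inputs from the sample size paragraph: SD of GFR change 15.97 (treated) and 12.18 (placebo), with ± read as SD; difference 15 ml/min; 38 per group. Two-sided 0.05 is assumed. SE = √(s_T²/38 + s_P²/38); power is from the noncentral t.

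| SDs used | SE | 15/SE | Power | Difference at 90% power |
|---|---|---|---|---|
| 15.97 in both arms | 3.66 | 4.09 | 98.1% | 12.0 |
| 15.97 and 12.18 | 3.26 | 4.60 | 99.5% | 10.7 |
| 15.97 and half of it | 2.90 | 5.18 | 99.9% | 9.5 |

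The stated 90% is not reproduced. Power is about 98% or more, and the same holds for the other three outcomes at their stated differences. That is a separate matter, but it shows that the t-test is not short of power on the plan's inputs.

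**2. Variance ratio, adjusted model to change score, at 38 and 38.** Scale the baseline SD to 1. Let ρ be the placebo slope (same SD at both visits), b the treated slope, and k the ratio of treated to placebo SD of change. The change-score variance is proportional to 2(1 − ρ)(1 + k²). At 1:1 the fitted common slope is about β = (ρ + b)/2, which gives

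ratio ≈ [1 − (1 − β)² / ((1 − ρ)(1 + k²))] × (1 + 1/72),

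where the last factor is the cost of estimating the slope. If the extra treated variance is unrelated to baseline, b = ρ and the bracket becomes (ρ + k²)/(1 + k²). For k = 2 and ρ = 0.7: 4.7/5 = 0.940, and × 1.014 = 0.953. Simulation with normal data (60,000 to 80,000 runs per cell) gave 0.952. Simulated ratios, with ρ assumed:

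| SDs of change | ρ 0.5 | 0.7 | 0.8 | 0.9 |
|---|---|---|---|---|
| 2:1, as the plan assumes | 0.911 | 0.952 | 0.975 | 0.993 |
| Pilot GFR, k = 15.97/12.18 = 1.31 | 0.825 | 0.902 | 0.941 | 0.979 |
| Equal | 0.754 | 0.861 | 0.914 | 0.966 |

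Under 2:1 SDs, a t-test with 90% power becomes 92.5, 91.4, 90.7 and 90.2%. For the first: 3.24/√0.911 = 3.40; 3.40 − 1.96 = 1.44, which is 92.5%.

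**3. Downside at 38 and 38.** The bracket cannot exceed 1, so the only loss is the slope-estimation factor, 1/72 = 1.4%. For ρ of 0.7 to 0.9, simulation gave 0.987 to 1.009 at b = 1.0 and 1.004 to 1.018 at b = 1.2.

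**4. GFR, as a rough gauge.** ρ = 1 − SD_change²/(2 SD_base²). The baseline SD is not given, so two values are assumed: 8 × √10 = 25.3 (the ±8 around 76 in the 10-patient losartan study, read as an SE) and 60/√12 = 17.3 (the 20 to 80 ml/min entry window, taken as uniform).

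| SD_base | SD_change (placebo) | ρ | Ratio, b = ρ |
|---|---|---|---|
| 25.3 | 12.18 | 0.884 | 0.969 |
| 25.3 | 7.985 | 0.950 | 1.004 |
| 17.3 | 12.18 | 0.753 | 0.919 |
| 17.3 | 7.985 | 0.894 | 0.992 |

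The result runs from a 0.4% loss to an 8% saving.

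**5. If allocation is really 2:1 (51 and 25, 2:1 SDs, ρ 0.7 to 0.9).** A common-slope model loses about 3 to 5% at b = 1.2 and 7 to 9% at b = 1.4. An arm-by-baseline term brings the loss below 2%. Ordinary model errors are conservative here (size 0.016 to 0.027), while HC2 robust errors with a common slope hold size (0.048 to 0.052). With the interaction, plain HC2 runs at 0.055 to 0.070 at these slopes, because it treats the mean baseline as fixed. At 38 and 38 ordinary errors hold size (0.049 to 0.052).

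**6. The secondary ANOVA.** With one value per visit and complete data, the group-by-time contrast is the difference in mean change, so F = t² for the pooled test on 74 df. Numerical checks gave 0.19209 for both at 38/38 and 1.76830 for both at 51/25. If the group main effect were tested instead, baseline is averaged in and the expected difference is halved. With equal SDs the noncentrality is multiplied by √((1 − ρ)/(1 + ρ)), so 90% power falls to about 47, 28, 19 and 11% at ρ of 0.5, 0.7, 0.8 and 0.9.

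**The case against.** The strongest reply is that nothing here is wrong. The plan names one valid test, power at its stated differences is already about 98% or more, and under its own SD assumption the saving is 5% of variance or less once ρ reaches 0.7. No conclusion of the trial would plausibly turn on that. The size rests on a correlation the documents do not supply. The GFR proxies are weak: one comes from an acute crossover study in 10 patients not described as selected for renal dysfunction, the other from an eligibility window for a calculated clearance when the outcome is iothalamate clearance. The simulations use normal data, so skewed hormones are untested. The ANOVA is labelled secondary and conditional on completeness.

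All of that stands, and it is why this is an improvement and not a defect. It does not remove the case for a change that needs no new data and has a bounded downside.

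Two stronger readings do not hold. A reader might infer that the unadjusted test is biased or invalid. Randomization makes it unbiased, and its simulated size at 38 and 38 was 4.8 to 5.4%. A reader might also infer that the plan offers the ANOVA as independent confirmation, or tests the diluted main effect. The documents say neither; they only leave the term unnamed.

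**Conclusion.** The point holds as a cheap improvement. At 1:1, adjustment saves about 9, 5, 3 and 1% of variance at assumed ρ of 0.5, 0.7, 0.8 and 0.9 under the plan's 2:1 SDs, and up to about 24% with equal SDs and ρ 0.5. The cost is one degree of freedom and at most about a 2% loss if the treated slope is 1 or more. For GFR the gain is probably at the low end. These figures assume normal data, equal placebo SD at both visits and, for the savings, extra treated variance unrelated to baseline. Validity here means the error rate of each single test; it does not extend to multiplicity or to withdrawals after randomization.

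The ANOVA remark is minor. It applies to hormones, echocardiography, walk test and questionnaire. It does not apply to creatinine and potassium, or to GFR and sodium excretion if the three clearance periods are entered separately.

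**What to change.** First reconcile the 2:1 and 38-and-38 statements in the sample size paragraph.

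- **If 1:1:** make the primary analysis a linear model of the follow-up value (latest available, as now) on arm and the baseline value of the same variable, using the mean of the three clearance periods for GFR and sodium excretion. Keep the t-test on change as a supporting analysis. Ordinary model errors suffice; robust errors are optional.
- **If 2:1:** use heteroscedasticity-robust errors and consider an arm-by-baseline term centred at the overall mean. If that term is used, adding (slope difference)² × baseline variance/N to the HC2 variance restores size to 0.048 to 0.050.
- **Secondary ANOVA:** name the tested term and the time points, and do not present it as separate support for outcomes with one value per visit.

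The cost is analysis wording only, settled before unblinding. The change-score SDs can stay as the sample-size basis. If robust errors are chosen, check that the SAS release named under Data Handling provides them.

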2. Chronic AT1 receptor blockade in subjects with compensated CHF and renal dysfunction will improve humoral function with suppression of the aldosterone and increase renal cGMP generation as compared to placebo.
3. Chronic AT1 receptor blockade in subjects with compensated CHF and renal dysfunction will improve left ventricular systolic and diastolic function and filling pressures as compared to placebo as evident by:
 - Improvement in ejection fraction

- Decrease in filling pressures with a decrease in the ratio of early mitral diastolic Doppler flow velocity (E) to tissue Doppler velocity (e') of the mitral annulus (E/e')
- Improved indices of diastolic function with an increase in the e' velocity (faster relaxation)
- Improvement in clinical status as measured by 6-min walk and MLWHFQ

Study design

This will be a **double-blinded placebo controlled study design**. Subjects will be randomized to the Chronic AT1 receptor blockade or to the placebo group. We will compare the effect of 12 weeks of Chronic AT1 receptor blockade with Candesartan (n=38) or placebo (n=38) on cardiorenal and humoral in subjects with compensated CHF and renal dysfunction

Specific methods

i) Study population

76 Subjects with compensated CHF with renal dysfunction

Inclusion Criteria:

- Left ventricular ejection fraction of equal or less than 40% assessed by echocardiography, nuclear scan, MRI or left ventriculogram within the past 48 months.
- Stable New York Heart Association (NYHA) class II and III symptoms as defined by: no change in NYHA symptoms over the past 3 months, on stable doses of ACE inhibitor, beta blocker, digoxin and furosemide over the last 4 weeks and no episode of decompensated CHF over the past 6 months.
- Calculated creatinine clearance of less than 90 ml/min and greater than 20 ml/min, using the MDRD formula assessed within the past 48 months and a confirmatory calculated creatinine clearance equal or less than 80 ml/min and greater than 20 ml/min at the time of enrollment.

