Sample size calculation: Preliminary data were obtained from the applicant's previous study. These data were used to estimate the standard deviation of the change in each parameter in the treated group. It was assumed that the standard deviation in the untreated group would be only $\frac{1}{2}$ of that in the treated group, since the treated group is composed of responders and non-responders, while the untreated group response data is largely due to biological and measurement variability between 2 occasions, with little or no actual signal. In light of this argument, allocation will be unequal in order to optimize the precision of the group comparison. Specifically, there will be 2 treated subjects per 1 placebo subject. Preliminary data for this analysis is provided below.

	Change from Baseline in AT1 group	Change from Baseline in Placebo group	N
GFR ml/min	-20.67 ± 15.97	1.13 ± 12.18	6
Na excretion mEq/min	-11.89 ± 27.27	-10.78 ± 20.08	6
ANG II pg/ml	29.32 ± 107	11.98 ± 43.67	6
Renin ng/ml/hr	4.9 ± 6.5	3.9 ± 4.4	6

So based on this preliminary data, the study will have **90% power** to detect the following differences using 38 patients in the AT1 receptor blocker group, and 38 in the placebo group.

	Detectable change	N/group
GFR ml/min	15	38 and 38
Na excretion mEq/min	25.4	38 and 38
ANG II pg/ml	100	38 and 38
Renin ng/ml/hr	6.1	38 and 38

Data Handling

The study coordinator will enter data into a Microsoft Excel spreadsheet. In addition to cardiorenal and humoral data mentioned above, 6 min walk, MLWHFQ scores and clinical data including cardiovascular risk factors, medications, clinical events, laboratory data and physical exam will be collected. Data will be stored on a

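### Hormone levels are compared by a t-test on raw change that ignores the measured baseline, and the plan does not say what to do if the assays are right-skewed

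*Combined protocol and SAP*

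**What the plan says.** Section iii), Sample size and statistical analysis, defines the primary analysis as "a comparison of the parameters of interest between the AT1 receptor blockade group and placebo". It names one method for all of them, to be carried out "using a two-sample t-test comparing the change from baseline" to the last available visit. The only other method is a secondary analysis, run if data are complete or nearly so: "The groups will be compared in this analysis using a 2 factor repeated measures analysis of variance". Neither includes a baseline covariate, and no transformation, rank method or distribution check appears anywhere.

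The Study protocol section has renin, aldosterone, angiotensin II, angiotensin 1-7, ANP and BNP drawn before randomisation, and repeats the humoral measurements at the end of week 12. Hypothesis 2 states that AT1 blockade "will improve humoral function with suppression of the aldosterone and increase renal cGMP generation as compared to placebo". The sample-size tables give angiotensin II and renin as raw changes, in pg/ml and ng/ml/hr.

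**The concern.** There are two separate issues.

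- **Baseline.** A change score subtracts the whole baseline value, which amounts to fixing the regression slope of follow-up on baseline at 1. When the correlation is below 1, that adds noise. ANCOVA estimates the slope and uses data already in hand.
- **Scale.** Hormone concentrations are positive and may be right-skewed, with treatment effects that act as ratios. If so, a few subjects with high levels can dominate the SD of raw change and weaken the test of the humoral hypothesis. If not, taking logs gains nothing and can lose power. The plan has no rule for either case, so the scale could end up being chosen after the results are seen.

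**Working it through.** **The plan's own figure.** For angiotensin II the plan claims 90% power "to detect the following differences using 38 patients in the AT1 receptor blocker group, and 38 in the placebo group", with a detectable difference of 100 pg/ml. Take the pilot AT1 SD of 107 in both arms and two-sided alpha 0.05 (the plan does not state sidedness). The standard error is 107 × √(2/38) = 24.5. Power is Φ(100/24.5 − 1.96) = Φ(2.11), or about 98%. The difference detectable with 90% power is about 81 pg/ml. The stated 90% therefore does not reproduce at 38 and 38, but it errs on the safe side. No shortfall against the plan's own angiotensin II target is shown.

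**Baseline adjustment.** Let both visits have variance σ² and correlation rho, with n per arm.
- Change score: Var = (2/n) × 2σ²(1 − rho)
- ANCOVA, large samples: Var = (2/n) × σ²(1 − rho²)
- Ratio: (1 − rho²) / [2(1 − rho)] = (1 + rho)/2

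The documents give no rho, so a range is shown. The last column multiplies the stated 100 pg/ml by the square root of the ratio.

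| Assumed rho | Variance ratio | Detectable difference, pg/ml |
|---|---|---|
| 0.3 | 0.65 | 81 |
| 0.5 | 0.75 | 87 |
| 0.7 | 0.85 | 92 |
| 0.9 | 0.95 | 97 |

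The planned secondary analysis does not recover this gain. With two visits and complete data, the group-by-time test in a repeated measures ANOVA is the change-score t-test squared.

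**Does the pilot table show skewness?** For angiotensin II the ratio of SD to mean change is 107/29.32 = 3.65 on AT1 blockade and 43.67/11.98 = 3.65 on placebo. For renin it is 6.5/4.9 = 1.33 and 4.4/3.9 = 1.13. For placebo GFR it is 12.18/1.13 = 10.8. A change can take either sign, so this ratio grows whenever the mean change is near zero and says nothing about shape. A weaker hint is that the angiotensin II SD and mean change are both about 2.45 times larger on AT1 blockade than on placebo (107/43.67 and 29.32/11.98), which would suit a multiplicative scale. With N = 6 the difference in SD is not firm (F-test p about 0.07).

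**Power by simulation.** Settings are 38 per arm and two-sided 0.05. All distributions are assumptions. In the log-normal rows, log SDs are 0.8 between and 0.4 within subjects. In the normal rows, the effect is an additive shift of 0.6 SDs of the change.

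| Assumed data | Raw change t-test | Raw ANCOVA | Log ANCOVA |
|---|---|---|---|
| Log-normal, 1.5-fold rise | 67% | 68% | 89% |
| Log-normal, fall to 1/1.5 | 51% | 68% | 90% |
| Normal, CV 0.3, rho 0.5 | 73% | 84% | 81% |
| Normal, CV 0.4, rho 0.8 | 74% | 77% | 64% |

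Raw ANCOVA is at least as powerful as the planned test in every row. Log ANCOVA is much better in the log-normal rows and worse in the last one. The 64% varies between about 61% and 64% with the treatment of the few simulated values at or below zero.

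**The case against.** The planned test is prespecified and valid under randomisation. In simulations of the log-normal scenarios with no treatment effect, its type I error was 3.6% to 5.1%. It estimates a difference in the units in which the plan sets its targets, whereas a log analysis estimates a ratio. Hypothesis 2 names aldosterone and renal cGMP generation. The pilot table has no aldosterone data, and cGMP generation can be negative, so it cannot be logged. All of this stands, and it makes the point an improvement and not the correction of an error.

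A reader might infer from 29.32 ± 107 that angiotensin II must be skewed and needs logs. The documents do not support that. The same reasoning would apply with more force to placebo GFR. Large falls from baseline are implausible only if baseline levels are low, and no baseline level is given. A reader might also infer that the humoral comparisons are underpowered as planned. The plan's own angiotensin II figures give about 98% power for its stated target.

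The objection does not reach baseline adjustment. That gain does not depend on skewness, keeps the raw units and needs no new data.

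**Conclusion.** The point holds as a low-priority improvement. The firm part is that the plan omits baseline adjustment for hormones measured at both visits. The treatment-effect variance would fall to 0.65 to 0.95 of its change-score value for an assumed rho of 0.3 to 0.9. That factor is a large-sample result with equal variances. The plan's sample-size text itself assumes a placebo SD half the treated one, so treat the factor as a guide.

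The log-scale part is conditional. It could raise power from about 51% to 90% for a fall to 1/1.5, the direction hypothesised for aldosterone, or lower it from about 74% to 64%. Nothing in the documents shows which case applies. A general claim that logs would be more precise goes further than they allow. What the plan lacks is a rule for choosing the scale.

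**What to change.** For renin, aldosterone, angiotensin II, angiotensin 1-7, ANP and BNP:

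1. Make the main comparison an ANCOVA of the week-12 level on arm and baseline level. Keep the two-sample t-test on change as a sensitivity analysis.
2. Before unblinding, record a rule for the scale, with its criterion for skewness written out. If the pooled blinded baseline values of a hormone are clearly right-skewed, use log level and log baseline and report the ratio of geometric means with a 95% CI. Otherwise stay on the raw scale. Baseline samples are drawn before randomisation, so looking at them pooled reveals nothing about treatment.
3. State how undetectable values are handled.
4. Keep renal cGMP generation on the raw scale. It is a difference between urinary excretion and filtered load and can be negative.

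The cost is a paragraph in the SAP and no extra data. The downside is that any hormone analysed on the log scale is reported as a ratio and no longer lines up directly with the raw-unit detectable differences in the sample-size table. The sensitivity analysis keeps that link.

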- Patients will have blood drawn to measure plasma creatinine and potassium 7-10 days after every dose increase until target dose is achieved. Thereafter, subjects will get blood draws every 4 weeks. *If there should be a potassium result <3.5 or >6.0, subjects will need to have labs redrawn the same day.*
- Subjects will also have access to a 24-hour phone number should they have any questions or develop any side effects.
- They will be instructed to measure their blood pressure weekly and record it, along with heart rate and weight.
- They will also receive a weekly phone call to review status.
- During the study, if patient develops symptomatic hypotension as defined above or an increased of plasma creatinine of > 0.3 mg/dL or hyperkalemia > 5.7 meq/ml, the dose will be reduced by 50%. If those parameters persist, the dose will be decreased further by 50%. At the discretion of the investigator, the medication can be discontinued

The following stopping rule will be applied to ensure patient safety

If the patients develop symptomatic hypotension as defined by systolic blood pressure of < 85 mmHg, with lightheadedness, dizziness or visual symptoms after the first dose of the medication in the CRU, the patient will be excluded from the rest of the study. During the study, if patient develops symptomatic hypotension as defined above or an increase in plasma creatinine of > 0.3 mg/dL or hyperkalemia > 5.7 meq/ml, the dose will be reduced by 50%. If those parameters persist, the dose will be decreased further by 50%. If those parameters persist, the subject will be withdrawn from the study

Other potential minor risk includes:

The risks of blood drawing include bleeding at the puncture site, bruising and pain. These risks occur in a very small portion of the population. We will exclude patients with hemoglobin of < 9 g/dL. The blood draw amount for this study is 200 mLs.

This protocol may be hazardous to an unborn child. There is no medical information to determine whether there are significant risks to a fetus carried by a mother who is participating in this study. Therefore, female

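### The secondary analysis runs only if the data turn out sufficiently complete, which treatment itself can affect; for outcomes with intermediate values, an unconditional mixed model would be better

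*Combined protocol and SAP*

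**What the plan says.** Section iii (Sample size and statistical analysis) gives two analyses.

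- Primary: "This analysis will be completed using a two-sample t-test comparing the change from baseline to the latest time point available". No completeness condition is attached.
- Secondary: "if complete or near complete data is available, a secondary analysis will be completed using all data from baseline", up to the last value on record. The method follows: "The groups will be compared in this analysis using a 2 factor repeated measures analysis of variance". The text gives no threshold for near completeness, covariance structure or rule for missing values. Data Handling names SAS 8.2 but no procedure.

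Intermediate values come from section ii (Study protocol). Laboratory timing follows each subject's titration: "Patients will get blood draw 7-10 days after each dose increase to measure plasma creatinine and potassium until target dose is achieved". After that, draws are four-weekly. Blood pressure, heart rate and weight are recorded weekly. The renal clearance and humoral measurements are scheduled only at baseline and at the twelve-week visit.

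On exits, the stopping rule under Potential risks and Protection against risk covers symptomatic hypotension, a creatinine rise above 0.3 mg/dL and potassium above 5.7. After two dose reductions it ends: "If those parameters persist, the subject will be withdrawn from the study". For the same situation, section ii says only that the investigator may discontinue the drug. Both sections remove subjects with symptomatic hypotension after the first dose, which is given after randomisation.

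**The concern.** Whether the secondary analysis is done at all is decided after the data are seen, against an undefined standard. That standard can itself be an effect of treatment. The exit criteria are the three harms that the protocol names as its main concern when candesartan is added: hypotension, hyperkalemia and raised creatinine. The more often the drug causes them, the less complete the data become.

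If the analysis is run, a standard repeated-measures ANOVA omits subjects with a missing time point. Those removed for a high creatinine would be omitted, and the remaining candesartan subjects would be those who tolerated the drug. At stake is the comparison over time of creatinine, potassium, blood pressure, heart rate and weight.

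**Working it through.** The plan gives no figure for the secondary analysis, so there is none to reproduce. Its 90% power statement concerns four parameters measured at two visits and does not enter here.

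**Which outcomes are affected.** With two time points, the ANOVA group-by-time test is the t-test on change, so F = t². On a simulated 38 + 38 data set, both equal 3.977. For GFR, sodium excretion, angiotensin II and renin, skipping the ANOVA therefore loses nothing on the group comparison of change. The point applies only to outcomes with intermediate values.

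**Draw times.** Dose doublings every 14 to 18 days fall on days 14–18 and 28–36. Adding 7 to 10 days puts the first draw on day 14 + 7 = 21 to 18 + 10 = 28, and the second on day 28 + 7 = 35 to 36 + 10 = 46. Both move or disappear if titration is held. An ANOVA would need these binned into nominal draws.

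**Size for creatinine.** The documents give no creatinine variability or expected rise, so every input except the arm size and the 0.3 mg/dL trigger is assumed: 38 per arm; six draws; 40%, 70%, then 100% of each subject's own change; measurement SD 0.10 mg/dL; between-subject SD of change 0.15 or 0.25; 2,000 simulated trials per row. Exit follows three successive rises above 0.3, which approximates a trigger followed by two failed reductions. Dose reduction is assumed not to lower creatinine. Shortfall = 1 − (complete-subject difference ÷ no-loss difference).

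| Mean rise on drug | SD | Withdrawn, drug / placebo | No-loss difference | Complete subjects | Shortfall | Latest value |
|---|---|---|---|---|---|---|
| 0.10 | 0.15 | 4.9% / 1.2% | 0.101 | 0.090 | 11% | 0.102 |
| 0.10 | 0.25 | 14.5% / 7.5% | 0.100 | 0.072 | 28% | 0.101 |
| 0.20 | 0.15 | 14.7% / 1.2% | 0.202 | 0.170 | 16% | 0.206 |
| 0.20 | 0.25 | 25.0% / 7.5% | 0.200 | 0.135 | 33% | 0.202 |
| 0.30 | 0.15 | 32.9% / 1.2% | 0.301 | 0.233 | 23% | 0.308 |
| 0.30 | 0.25 | 39.1% / 7.7% | 0.301 | 0.188 | 38% | 0.305 |

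With no true rise there is no bias. The last column is the primary analysis applied to creatinine; it recovers the no-loss difference to within about 2%.

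**Sensitivity to the exit rule, and the alternative model.**

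- Four draws and mean rises of 0.10 to 0.20: the shortfall is about 10–11% with a three-rise exit and about 30% with a two-rise exit. A mixed model on all available values is within about 2% and 7% of the no-loss value respectively.
- Two-rise exit, some exits after one rise, about 5% other loss, SD 0.15: complete subjects give 0.083, 0.116 and 0.155 against 0.105, 0.149 and 0.204. The shortfalls are 1 − 0.083/0.105 = 21%, 1 − 0.116/0.149 = 22% and 1 − 0.155/0.204 = 24%. The mixed model gives 0.101, 0.145 and 0.195, within 5%.

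For mean rises of 0.10 to 0.20, the range is roughly 10 to 30%.

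**The case against.** The strongest objection is that the primary analysis already covers the harm. It has no completeness condition, and for a withdrawn subject it uses the last value on record, including the one that led to exit. This stands. A reader might infer that the plan would hide a creatinine or potassium effect altogether; the documents do not support that, and the last column of the table shows why.

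The efficacy hypotheses and sample size concern outcomes assessed at two visits, and the plan does not expressly list creatinine, potassium or blood pressure among its parameters of interest. This also stands and limits the importance of the point. If those outcomes are not meant to be covered, the plan has no stated group comparison for them, and naming them would settle it.

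Dropping subjects and needing common time points are properties of the standard method, not statements in the plan. The phrase about using all data, with no procedure named, leaves room for a likelihood fit that keeps partial records. This is fair: loss of subjects is a possible result, not a stated one. But nothing specifies such a fit, and a completeness condition suggests a method that needs complete data.

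Finally, the condition might screen out the worst cases, since 25% withdrawn is hardly near complete. That holds only in part. With 4.9% withdrawn on candesartan and 1.2% on placebo, which could pass as near complete, the shortfall is still 11%, though only 0.101 − 0.090 = 0.011 mg/dL.

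**Conclusion.** The point holds as a low-cost improvement to a secondary analysis. The condition has no threshold, completeness can depend on treatment, and the named method in its standard form keeps only complete subjects. For outcomes with intermediate values, the analysis may be skipped or may understate harm. For creatinine the understatement is roughly 10 to 30% at assumed mean rises of 0.10 to 0.20 mg/dL, more at 0.30, and nil if the drug has no effect. These figures depend on the assumed variability, on the exit rule, and on dose reduction not reversing the rise. They support the direction more firmly than the size. Potassium and blood pressure were not simulated.

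Two broader inferences should not be drawn. The sentence does not bias the comparisons of GFR, sodium excretion, angiotensin II or renin: a subject who leaves before week 12 without an exit assessment has no post-baseline value for these in either analysis. Nor are creatinine and potassium the only measures between visits, since blood pressure, heart rate and weight are recorded weekly.

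**What to change.** Delete the completeness condition and replace the secondary analysis with:

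> Outcomes with intermediate values (plasma creatinine, potassium, blood pressure, heart rate, weight) will be analysed, whatever the completeness, by a linear mixed model on all randomised subjects with any post-baseline value. Fixed effects are arm, nominal draw (or time since first dose), arm-by-time and the baseline value; within-subject correlation will be modelled. The number in each arm with no post-baseline value, including first-dose exclusions, will be reported.

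The last sentence is needed because subjects removed after the first dose have no post-baseline creatinine or potassium and fall outside any such model.

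The study protocol section (discretionary discontinuation of the drug) and the stopping rule (withdrawal from the study) must also be reconciled, because the choice determines whose values continue to be collected.

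The cost is a short text change and a standard procedure on data already planned. The downside is that the model assumes data missing at random. That is a weaker assumption than a complete-subject ANOVA needs, and it is plausible where recorded values trigger withdrawal. It is less secure for discretionary exits.
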